6.4. Derived and Transformed Data

6.4.1. Baseline Definition

In general, baseline assessment is defined as the last non-missing result on or prior to the administration of the first dose of study medication. Baseline definitions for different variables during specific stages of the study are provided in [Table 3](#).

Table 3: Baseline Visit by Study Stage, Cohort, and Variable

Cohort	Assessment at Screening (V1, Days -28 to -1)	Assessment at Baseline (V2, Day 0)	Result Used as Baseline
Safety Data (including vital signs, laboratory data, ECG, PEs, etc) During Stages 1 and 2			
Cohort 1	X	X	Baseline is the last result obtained on/prior to V2; If result from V2 is unavailable, then use V1.
Note: Safety results for Stages 1 and 2 were reported in iCSR-1 and will not be repeated here.			
Safety Data During Stage 2 Period 5 and Stages 3 and 4			
Cohort 1	X	X	Baseline is the last result obtained on/prior to the start of the 20 mg/kg ATB200 + 260 mg AT2221 dose in Stage 2 Period 5. If the result from V9 is unavailable, then use V8. See Section 6.4.5 .
Cohorts 2, 3, and 4	X	X	Baseline is the last result obtained on/prior to V2. If result from V2 is unavailable, then use V1.
Efficacy Data, Biomarkers, and PROs During Stage 2 Period 5 and Stages 3 and 4			
Cohorts 1, 2, 3, and 4	NA	X	Baseline will be the result obtained at V2.

Abbreviations: ECG = electrocardiogram; NA = not applicable; PEs = physical examinations (which includes brief physical examination and comprehensive physical examination); PROs = patient-reported outcomes; V = visit

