6.4.3. Change from Baseline and Percent Change from Baseline

Analysis of change from baseline will include only subjects who have assessment at both baseline and the post-baseline time point being analyzed. That is:

- Change from baseline is calculated as: Change = post-baseline result – baseline result.
- Percent change from baseline is calculated as: $100 * (\text{Change from baseline} / \text{Baseline result})$.

If either the baseline or the post-baseline result is missing, the change from baseline and the percentage change from baseline are set to missing.

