^b Cohort 1 target day for Month X (starting from V9) is determined as (X * 30) + 43. For example, the target day for Month 3 is approximately at Day 3 * 30 + 43 = 133.

^c For safety analysis by visit, baseline is taken from Visit 9 (Day 85), but for efficacy, biomarker, and PRO analyses, baseline value is taken from Visit 2 (Day 1). See Section 6.4.1 and Section 6.4.5.

^d Tx is the target day of planned assessment visit at Month X.

- If the derivation starts from the original study day at V2, then: T_{MONTH X} = (30 * X + 127). For example, the target day at Month 54 = T_{MONTH 54} = 30 * 54 + 127 = 1747. Target day of the assessment visit immediately before Month X is given by T_{BEFORE}. For example, T_{BEFORE} = T₄₈ = (30 * 48 + 127) = 1567. Target day of the assessment visit immediately after Month X is given by T_{AFTER} = T₆₀ = (30 * 60 + 127) = 1927. The visit windows are then given as d1 – d2, where d1 = ([T_{BEFORE} + T_{MONTH X}] / 2) + 1 and d2 = (T_{MONTH X} + T_{AFTER}) / 2.
- If the derivation starts from Visit 9, then target day at Month X is given by T_{MONTH X} = (30 * X + 43). For example, the target day at Month 54 is T_{MONTH 54} = 30 * 54 + 43 = 1663. Target day of the assessment visit immediately before Month X is given by T_{BEFORE}. For example, T_{BEFORE} = T₄₈ = (30 * 48 + 43) = 1483. Target day of the assessment visit immediately after Month X is given by T_{AFTER} = T₆₀ = (30 * 60 + 43) = 1843. Visit windows are given as d3 – d4, where d3 = ([T_{BEFORE} + T_{MONTH X}] / 2) + 1 and d4 = (T_{MONTH X} + T_{AFTER}) / 2.

^e LAV represents the result obtained from the subject’s last visit of assessment. Summary at the LAV will only be provided for the efficacy analyses.

Efficacy data will be summarized at: Baseline (Visit 2), Visit 12, Month 3, Month 6, Month 9, Month 12, Month 15, Month 18, Month 21, Month 24, and every 6 months thereafter in Stage 4. Safety data will be summarized at: Baseline (Visit 9), Visit 10, Visit 11, Visit 12, Month 3, Month 6, Month 9, Month 12, Month 15, Month 18, Month 21, Month 24, and every 6 months thereafter in Stage 4.

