9.4.2. Muscle Strength Tests

The MMT summary scores will be provided for the following:

- Body part (shoulder, elbow, knee, and hip)
- Proximal muscles (shoulder and hip)
- Body side (lower, upper)
- Total MMT

Ambulatory subjects were expected to perform all muscle tests, while non-ambulatory subjects were to perform only the upper body muscle tests.

The MMT score at each visit is calculated only if the subject has the corresponding test scores for all applicable muscle groups. The MMT scores will be analyzed as continuous variables at each scheduled visit. The actual score and absolute change from baseline in the MMT scores will be summarized. No percent change from baseline analysis will be performed for the MMTs. A listing of the data for all MMT scores (including individual scores and summary scores) will be provided.

The QMTs will be summarized for the body part, proximal muscles, body side, and total. The actual value, absolute change, and percent change from baseline in the QMT values will be presented. A listing of the data for all QMTs including individual scores and summary scores will be provided.

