9.7. Handling of Dropouts or Missing Data

The efficacy and safety analysis will be based on observed values. However, summary at the LAV will be provided for the efficacy analyses (see Section [6.5](#)).

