APPENDIX 1. DESCRIPTIONS AND DERIVATIONS OF EFFICACY ENDPOINTS

1. Pulmonary function tests (PFTs):

- Sitting forced vital capacity (FVC): maximum FVC (L) and percent predicted FVC (%)
- Supine forced vital capacity: maximum FVC (L) and percent predicted FVC (%)
- Maximum inspiratory pressure (MIP) (cm of water [cm H₂O])
- Maximum expiratory pressure (MEP) (cm of water [cm H₂O])
- Sniff nasal inspiratory pressure (SNIP) (cm of water [cm H₂O])
- The percent predicted values of MIP, MEP, and SNIP will be calculated as:
$$\% \text{ predicted} = (\text{actual result} / \text{predicted result}) * 100.$$

The predicted results are obtained using the following reference equations: [Uldry and Fitting, 1995](#) for MIP, MEP, and the lower limit of normal (LLN), and [Evans and Whitelaw, 2009](#) for the SNIP values.

Table 12: Predicted Equations for MIP, MEP, and SNIP

PFT	Male	Female
MIP	$120 - (0.41 \times \text{Age in years})$	$108 - (0.61 \times \text{Age in years})$
MIP LLN	$62 - (0.15 \times \text{Age in years})$	$62 - (0.50 \times \text{Age in years})$
MEP	$174 - (0.83 \times \text{Age in years})$	$131 - (0.86 \times \text{Age in years})$
MEP LLN	$117 - (0.83 \times \text{Age in years})$	$95 - (0.57 \times \text{Age in years})$
SNIP	$126.8 - (0.42 \times \text{Age in years})$	$94.9 - (0.22 \times \text{Age in years})$

Abbreviations: LLN = lower limit of normal; MEP = maximum expiratory pressure; MIP = maximum inspiratory pressure; PFT = pulmonary function test; SNIP = sniff nasal inspiratory pressure

2. Manual muscle testing (MMT):

- Right/left shoulder adduction
- Right/left shoulder abduction
- Right/left elbow flexion
- Right/left elbow extension
- Right/left hip flexion – ambulatory patients only
- Right/left hip abduction – ambulatory patients only
- Right/left hip adduction – ambulatory patients only
- Right/left knee flexion – ambulatory patients only
- Right/left knee extension – ambulatory patients only

Each manual muscle testing is evaluated on a scoring scale from 0 to 5: 0 = no muscle movement; 1 = visible muscle movement, but no movement at the joint; 2 = movement at the joint, but not against gravity; 3 = movement against gravity, but not against added resistance; 4 = movement against resistance, but less than normal; 5 = normal strength.

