- Upper body muscle groups include right/left shoulder abduction, right/left shoulder adduction, right/left elbow flexion, and right/left elbow extension with the total score ranging from 0 – 40, based on these 8 muscle groups. That is,
Upper = Shoulder + Elbow.
- Lower body muscle groups include right/left hip flexion, right/left hip abduction, right/left hip adduction, right/left knee flexion, and right/left knee extension with the total score ranging from 0 – 50, based on these 10 muscle groups. That is,
Lower = Hip + Knee.
- Proximal body muscle groups include right/left hip flexion, right/left hip abduction, right/left hip adduction, right/left shoulder abduction, and right/left shoulder adduction with the total score ranging from 0 – 50, based on these 10 muscle groups. That is, Proximal = Shoulder + Hip.
- Total MMT score ranges from 0 – 90 based on all 18 muscle groups, and it will be analyzed as a continuous variable. Higher scores indicate less disease impact on muscle functions. That is, Total = Upper + Lower.

Note: If there are many instances of missing testing scores (ie, if $\geq 50\%$ of the testing scores [at least 9 out of 18] are missing), then the total will be normalized to 100%. That is, the total score will be prorated as: Total = (Mean of all available scores) $\times 18$.

Note: The right/left hip adduction muscle group was added later in the study, and so it will not appear in MMT summaries provided at earlier time points in Stage 3. For example, the lower body score at the earlier time points will range from 0 – 40 (based on 8 muscle groups) and the total MMT score at the earlier time points will range from 0 to 80 (based on 16 muscle groups).

Ambulatory subjects were expected to perform all the muscle tests for both lower and upper body, while non-ambulatory subjects were to perform the muscle tests for only upper body.

- Body parts are shoulder, elbow, knee, and hip.

Note: Each body part is the sum of its corresponding 4 muscle groups,
eg, shoulder = right/left shoulder abduction + right/left shoulder adduction.

3. Quantitative muscle tests (QMTs) using hand-held dynamometer (in kg):

- Right/left shoulder adduction
- Right/left shoulder abduction
- Right/left elbow flexion
- Right/left elbow extension
- Right/left hip flexion – ambulatory patients only

- Right/left hip adduction – ambulatory patients only
- Right/left hip abduction – ambulatory patients only
- Right/left knee flexion – ambulatory patients only

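### MMT change from baseline can subtract a 16-group Visit 2 score from an 18-group later score, and the SAP has two conflicting rules for missing MMT scores

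*SAP*

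**What the plan says.** SAP Appendix 1, item 2, grades each muscle group from 0 to 5. It defines the total on 18 groups (0 to 90), lower body on 10 (0 to 50), proximal on 10 (0 to 50) and upper body on 8 (0 to 40). The list of groups includes "Right/left hip adduction – ambulatory patients only". A note then says that "The right/left hip adduction muscle group was added later in the study, and so it will not appear in MMT summaries provided at earlier" Stage 3 time points, and that "the total MMT score at the earlier time points will range from 0 to 80 (based on 16 muscle groups"). The same note puts the earlier lower-body score at 0 to 40 on 8 groups.

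Three other places define the change score:

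- Table 3 in Section 6.4.1, for efficacy data in all cohorts: "Baseline will be the result obtained at V2".
- Section 6.4.3: "Change from baseline is calculated as: Change = post-baseline result" minus the baseline result.
- Section 9.4.2: "The actual score and absolute change from baseline in the MMT scores will be summarized".

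The last assessed value (LAV) is a further efficacy time point. Section 9.7 says that "summary at the LAV will be provided for the efficacy analyses", and a footnote to Table 4 repeats this.

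On missing scores, Section 9.4.2 calculates an MMT score only if every applicable muscle group was tested. Appendix 1 prorates the total, as the mean of the available scores × 18, when at least 9 of the 18 are missing.

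**The concern.** The SAP acknowledges two score ranges but does not carry that into the change score. If Visit 2 was scored on 16 groups and a later visit on 18, the difference contains the two added grades as well as any change in strength. Added grades are never negative, so the error always favours apparent improvement or hides decline. It falls on later visits, which are what the final report is meant to describe. Mean change and, where appropriate, its 95% confidence interval (Section 6.2.1) would absorb it.

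The two missing-score rules are a separate problem: two programmers who follow different sections would produce different MMT totals.

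**Working it through.** **1. The SAP's own ranges.** Maximum = 5 × number of groups.

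| Score | Earlier | Later |
|---|---|---|
| Total | 16 × 5 = 80 | 18 × 5 = 90 |
| Lower body | 8 × 5 = 40 | 10 × 5 = 50 |
| Proximal | 8 × 5 = 40 | 10 × 5 = 50 |
| Upper body | 8 × 5 = 40 | 8 × 5 = 40 |

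The stated ranges reproduce. The SAP does not state the earlier proximal range; it follows from removing right and left hip adduction from the 10 proximal groups.

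**2. Change at constant strength.** If all grades are the same at both visits, later score − Visit 2 score = right + left hip-adduction grade = 2 × grade when the sides are equal.

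- Grade 3: 2 × 3 = +6
- Grade 4: 2 × 4 = +8
- Grade 5: 2 × 5 = +10

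With grade 4 throughout, the total goes from 16 × 4 = 64 to 18 × 4 = 72. Lower body and proximal each go from 8 × 4 = 32 to 10 × 4 = 40. The true change is 0. On the total, +8 would offset a real loss averaging 8 / 16 = 0.5 grade in each original group.

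**3. A decline that is hidden.** Suppose every leg group falls from grade 4 to grade 3. Visit 2 lower body = 8 × 4 = 32. On the same 8 groups the later score is 8 × 3 = 24, a change of −8. On 10 groups it is 10 × 3 = 30, a change of −2.

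**4. Who has a 16-group baseline.** Hip adduction is absent from earlier Stage 3 time points, and Cohort 1's Visit 2 precedes Stage 3, so Cohort 1 baselines have 16 groups. For Cohorts 3 and 4 it depends on whether a subject enrolled before or after the addition, and no date is given. Protocol Section 10.2.21 lists hip adductors for the dynamometer only, so it does not date the MMT addition. Cohort 2 has upper-body tests only.

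**5. Whether another rule catches it.**

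- If applicable in Section 9.4.2 means applicable at that visit, a 16-group baseline stands and the mismatch remains. If it means all 18 groups, 16-group baselines have no score, which contradicts the 0 to 80 total in Appendix 1.
- The proration note does not rescale early totals: 2 / 18 = 11.1% missing, below its 50% trigger.
- The note that each body part sums 4 muscle groups conflicts with a lower-body score made of hip plus knee on 10 groups. Knee has 4, so hip must have 6. It is therefore unclear whether the hip score includes adduction.

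**6. The missing-score rules together, for an ambulatory subject at an 18-group visit.**

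| Missing of 18 | Section 9.4.2 | Appendix 1 |
|---|---|---|
| 0 | score | score |
| 1 to 8 | no score | no rule stated |
| 9 to 17 | no score | prorated total |

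Read together, sparse data would be scored and nearly complete data would not. This is the reverse of the SAP's rule for the Rotterdam Handicap Scale and Fatigue Severity Scale, which prorates only when at least 5 of 9 items are present. Cohort 2 has 8 of 18 groups by design, so 10 / 18 = 55.6% are absent. Read literally, the note turns a grade-4 upper-body sum of 8 × 4 = 32 into a total of 4 × 18 = 72.

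**The case against.** The strongest reply is that little depends on these scores. No hypothesis is tested, MMT is one of many descriptive efficacy endpoints, and upper-body, shoulder, elbow and knee scores are unaffected. Individual MMT grades will be listed, so a matched change could be recovered. The dataset specifications and table shells to which the SAP refers are not among the documents and may contain a matching rule. The inequality in the proration note may also simply be inverted. All of this limits the weight of the point. It does not supply the missing rule in the SAP, and an inverted proration rule would still contradict Section 9.4.2.

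A reader might infer three stronger things that the documents do not support.

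- **A count of affected visits.** One could combine the dynamometer-only text with the August 2018 cut-off of the protocol's interim tables and treat visits shown there as free of the problem. Those tables cover 6MWT and FVC, not MMT, and stop at Month 18, where Cohort 1 has 9 of 10 and 8 of 9 subjects. The protocol text is dated January 2019, and Table 4 of the SAP runs on to an open-ended Month X. No secure bound follows.
- **A shift in a cohort or pooled mean.** The number of subjects affected is unknown, and any subject in Cohorts 3 or 4 who enrolled after the addition has an 18-group Visit 2 and no artefact.
- **A percentage inflation.** The general endpoint list in Section 4.4 names percent change for muscle tests, but Section 9.4.2 specifically excludes it for MMT. Only the point shifts matter.

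**Conclusion.** The point holds as a gap in specification that should be fixed. Following the stated rules, an ambulatory subject with a 16-group Visit 2 gains 2 × the hip-adduction grade in the total, lower-body and proximal scores without any change in strength. This occurs at visits after the addition, and at the LAV when the last visit falls after it. The figures of +6, +8 and +10 assume equal right and left grades of 3, 4 and 5; the −2 in place of −8 is an illustration. Exposure is established for Cohort 1 baselines and is conditional on enrolment date for Cohorts 3 and 4. The numbers of visits and subjects cannot be derived. The contradiction between Section 9.4.2 and the proration note rests on the text alone.

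**What to change.** - Compute change from Visit 2 in the MMT hip, lower-body, proximal and total scores on the 16 groups tested at both visits, including at the LAV (lower body 0 to 40, proximal 0 to 40, total 0 to 80). With 4 hip groups, the body-part note is then consistent.
- Report hip-adduction grades separately, or label any 18-group visit scores as such, and state when the test was added.
- Delete the proration for at least 9 of 18 missing, so that Section 9.4.2 governs, and state that Cohort 2 has no total MMT score.

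The cost is wording in Appendix 1 and derivation code, with no new data. Section 2 allows SAP changes before database lock. The downside is that hip-adduction grades do not contribute to the change scores.

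Two side notes on the same appendix. The R-PAct total sums observed items, so read literally a blank counts as 0, the worst answer (17 × 2 = 34 instead of 36); set totals with blank items to missing. Ten PROMIS dyspnea items scored 0 to 3 give a range of 0 to 30, not 10 to 50.

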9.5. Patient-reported Outcomes

For each PRO instrument including R-PAct scale, RHS, FSS, and PROMIS scales, the total score is obtained by summing up the individual scores. Summaries will be provided at baseline, Visit 12 and every 3 months in Stage 3, and every 6 months in Stage 4. The actual total score, absolute change, and percent change from baseline in the total score at each visit will be summarized at each visit. The PROMIS scale was introduced in the middle of the study and so baseline scores will not be available. A subject listing of each individual PRO will be provided.

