 - Gowers' maneuver test is based on the subject lying down on the floor, then rising from the floor to get to a standing position. This is scored as: 1 = normal; 2 = butt first maneuver, one hand on floor; 3 = butt first maneuver, two hands on floor; 4 = unilateral hand support on thigh; 5 = bilateral hand support on thighs; 6 = arises only with aid of an object (table, chair, etc); 7 = unable to rise.

- Chair test is based on the subject arising from a sitting position in a chair to a standing position. This is scored as: 1 = normal; 2 = with wide base and/or difficulty but without support; 3 = with support on one thigh; 4 = with support on both thighs; 5 = with support on arms of chair or on a table; 6 = not possible.

GSGC was performed by ambulatory subjects only. The total GSGC score ranges from 4 (normal performance) to 27 (worst performance).

6. Other motor function tests – ambulatory subjects only

For each of these motor function tests, the actual time (in seconds [s]) that the subject takes to perform the test and the assigned score (which indicates the level of difficulty with which the patient performed this task) are recorded for analysis.

- Gowers' maneuver test is based on the patient lying down on the floor, then rising from the floor to get to a standing position. The time is measured in seconds (s) and assigned the test score.
- 10-meter walk test (10MWT) is based on the time it takes the subject to walk 10 meters. The score from this test is used as the Gait score in GSGC.
- 4-stair climb is based on the subject climbing 4 stairs.
- Timed Up and Go (TUG) test represents the time it takes the subject to stand up from the chair, walk to the line on the floor (about 3 meters), turn around, walk back to the chair, and sit down, all at the regular pace.

7. Rasch-built Pompe-specific Activity (R-PAct) consists of 18 questions, each scored on a scale from 0 = 'no,' 1 = 'yes, but with difficulty,' to 2 = 'yes, without difficulty.'

The 'summed raw score' or total score ranges from 0 to 36, with higher values representing lower level of disease impact on the muscles. The total score will be calculated simply by summing up the observed scores across the 18 items. The total score is analyzed as a continuous variable.

8. Rotterdam Handicap Scale (RHS): This consists of 9 questions, each scored on a scale from 1 = 'unable to perform task' to 4 = 'able to perform task independently or completely.'

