The total score ranges from 9 to 36, with higher values representing lower level of handicap. The total score is obtained as the sum of the individual scores, and it will be analyzed as a continuous variable. The instrument will be scored using the traditional 50% response rule, described as follows:

If a score of '0 = not applicable' is provided, it is interpreted as a missing response or an unanswered question.

If $\geq 50\%$ of the questions were answered (ie, at least 5 out of 9 responses are available), the total score is obtained as: Total = $([\text{Sum of all available scores}] \times 9) / (9 - [\text{Number of missing items}]) = (\text{Mean of all available scores}) \times 9$ ([Merkies, Schmitz et al. 2002](#)).

Otherwise (ie, if less than or equal to 4 out of 9 questions were answered), the total score will be considered missing ('.').

9. Fatigue Severity Scale (FSS): This consists of 9 questions, each scored on a scale from 1 = ‘completely disagree’ to 7 = ‘completely agree.’

The total score ranges from 9 to 63, with higher values representing higher level of fatigue due to the disease condition. The total score is obtained as the sum of the individual scores, and it will be analyzed as a continuous variable. The 50% response rule will be applied.

If at least 5 out of 9 item responses are available, the total score will be calculated as: $\text{Total} = ([\text{Sum of all available scores}] \times 9) / (9 - [\text{Number of missing items}]) = (\text{Mean of all available scores}) \times 9$. Otherwise, the total is considered missing.

10. PROMIS® Short Forms:

- PROMIS – Physical Function Short Form 20a (v2.0) consists of 20 questions. The first 14 questions are each scored on a scale from 1 to 5 as follows: 1 = unable to do; 2 = with much difficulty; 3 = with some difficulty; 4 = with a little difficulty; 5 = without any difficulty; the next 6 questions are each scored on a scale from 1 to 5 as follows: 1 = cannot do; 2 = quite a lot; 3 = somewhat; 4 = very little; 5 = not at all.

The total score ranges from 20 – 100, with higher scores indicating more mobility.

- PROMIS – Fatigue Short Form 8a consists of 8 questions, each scored on a scale from 1 to 5 as follows: 1 = not at all; 2 = a little bit; 3 = somewhat; 4 = quite a bit; 5 = very much; and 2 questions, each scored on a scale from 1 to 5 as follows: 1 = never; 2 = rarely; 3 = sometimes; 4 = often; 5 = always.

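### R-PAct totals sum only the answered items, so a blank scores the same as 'No' and can create a false decline or a false improvement

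*SAP*

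**What the plan says.** SAP Appendix 1 item 7 describes the instrument ("Rasch-built Pompe-specific Activity (R-PAct) consists of 18 questions") and its coding ("each scored on a scale from 0 = 'no,' 1 = 'yes, but with difficulty", with 2 for able without difficulty). It gives the range and direction as "total score ranges from 0 to 36, with higher values representing lower level of disease impact on the muscles". The scoring rule is: "The total score will be calculated simply by summing up the observed scores across the 18 items".

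Other parts of the SAP bear on the same total:

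- Section 9.5 repeats the plain sum for all the patient-reported instruments: "the total score is obtained by summing up the individual scores".
- Section 9.7 says only that observed values are used, with a summary at the last assessed value for efficacy.
- Section 6.4.3 sets change from baseline to missing when the baseline or post-baseline result is missing. It does not address a result built from an incomplete form.
- Appendix 1 item 8 (RHS) says: "The instrument will be scored using the traditional 50% response rule". Item 9 (FSS) says: "The 50% response rule will be applied", and then: "If at least 5 out of 9 item responses are available, the total score will be calculated as" the mean of the available items times 9, and otherwise missing.
- Section 9.4.2 gives an MMT score only when all applicable muscle groups were tested.

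Change and percent change in the R-PAct total are listed efficacy endpoints in SAP Section 4.4.

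**The concern.** Zero is a real answer on this scale, and it is the worst one. A sum over answered items therefore cannot distinguish a blank from a 'No'. A partly completed form still yields a number, so the safeguard in Section 6.4.3 is never triggered.

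Change from baseline then mixes functional change with item non-response. The R-PAct total is summarised visit by visit and at the last assessed value, in cohorts planned at 10 to 12, 4 to 6, 5 and 6 to 8 subjects (Protocol Section 9.1). At those sizes, one or two incomplete forms can move a cohort mean. RHS and FSS, the two instruments listed directly after R-PAct in Appendix 1, are protected against this, and no reason is given for treating R-PAct differently.

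**Working it through.** **Inputs.** K = 18 items, coded 0, 1 or 2 (SAP Appendix 1 item 7). The prorating formula is that of items 8 and 9, with 18 in place of 9. The answer patterns below are assumptions, because the documents give no item-level data.

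**The plan's own figure.** Range = 18 × 0 to 18 × 2 = 0 to 36, which reproduces the stated range.

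**Effect of one blank.** Observed-sum total = true total minus the true values of the blank items. Each blank therefore removes 0, 1 or 2 points.

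**Stable subject, complete form at the other visit, blanks with the same average as the answered items.** With *m* blanks:

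- gap after baseline: percent change = -m/18
- gap at baseline: percent change = +m/(18 - m)

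| Blanks | Observed sum (true total 27) | Gap after baseline | Gap at baseline |
|---|---|---|---|
| 1 | 25.5 | -5.6% | +5.9% |
| 2 | 24 | -11.1% | +12.5% |
| 4 | 21 | -22.2% | +28.6% |
| 9 | 13.5 | -50.0% | +100% |

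For two blanks: 1.5 × 18 = 27 and 1.5 × 16 = 24, so (24 - 27)/27 = -11.1% and (27 - 24)/24 = +12.5%. A concrete pattern is nine items at 2 and nine at 1, with one of each skipped. Prorating gives 24/16 × 18 = 27, so there is no false change.

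**Cohort mean.** In a cohort of 5, one subject whose true answers are all 2 and who leaves four items blank after baseline shifts the mean change by -(4 × 2)/5 = -1.6 points.

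**Items of unequal difficulty.** The form in Protocol Appendix 3 runs from combing hair to running, so the uniform pattern is not guaranteed. Two assumed patterns show the opposite problem:

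- Items 1 to 9 are truly 2 and items 10 to 18 truly 0, for a true total of 18. Four of the last nine are skipped. The observed sum is 18, which is correct. Prorating gives 18/14 × 18 = 23.1, which is 29% too high.
- A wheelchair-bound Cohort 2 subject (Protocol Table 11 schedules R-PAct for this cohort) leaves six items blank whose true answer is no, and averages 1 on the other 12. The observed sum is 12, which is correct. Prorating gives 12/12 × 18 = 18, which is 50% too high.

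The observed sum is thus right only when every blank would have been a 'No'. Prorating is right only when the blanks would have averaged the same as the answered items.

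**The case against.** The strongest reply is that item 7 may only be choosing the raw total over a Rasch-converted score, and assumes complete forms. On that reading the SAP is silent on blanks and does not plan to score them 0. This reading is possible, but the rule refers to observed scores and states no completeness condition. It would also leave the programmer to decide: in SAS, a SUM function ignores blanks, while adding with plus signs returns missing.

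Several other points stand in whole or in part:

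- The RHS comparison is weaker than it looks. RHS has a not-applicable response that needs a rule, and R-PAct has none. The FSS comparison does stand.
- R-PAct is not alone. The PROMIS totals in Appendix 1 item 10 are also plain sums with no rule for missing items.
- Mean prorating is not neutral for this instrument, as the last two examples show, and the instrument's own scoring instructions are not in the documents.
- Forms are completed at the visit before other procedures (Protocol Section 10.2.9), and missing eCRF data must be explained (Protocol Section 14.1.1). Blanks may therefore be few.
- The analysis is descriptive with no hypothesis test, and each patient-reported outcome is listed by subject.

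A reader might infer that every missing item shows as functional decline. The documents do not support that: a baseline gap has the opposite sign, and a blank whose true answer is 0 changes nothing.

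**Conclusion.** The rule as written gives a wrong total on any incomplete form where a blank would have been answered 1 or 2, and no other section corrects it. The error is bounded at 2 of 36 points per missing item. It is a false decline when the gap is after baseline and a false improvement when it is at baseline. If the same items are blank at both visits and the subject is stable, the false point change cancels.

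The -11.1% and +12.5% figures assume two blanks at one visit only, a stable subject, and blanks with the same average as the answered items. They are illustrations. With no item-missing rate in the documents, neither the net direction nor the size of bias in this study can be stated, and if all forms are complete the effect is zero. Nor should a reader conclude that prorating alone removes the bias. This affects the accuracy of a descriptive efficacy summary and should be corrected, but it does not threaten the study's conclusions as a whole.

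**What to change.** Before database lock, replace the scoring sentence in SAP Appendix 1 item 7 so that blanks are not scored 0. Use the rule already applied to RHS and FSS: if at least 9 of the 18 items are answered, total = mean of available items × 18; otherwise the total is missing. Apply it identically at baseline and at every later visit.

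Add two outputs:

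- a sensitivity summary of change from baseline restricted to fully completed forms, because the items differ in difficulty and prorating can overstate the total when hard items are skipped;
- the number of incomplete R-PAct forms by visit, so that a reader can judge whether the choice of rule matters.

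The cost is a short SAP edit, a small code change, one extra table and the incomplete-form counts. A few totals may become missing.
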